Hypothesis I-a: C-tDCS will be safe in AIS patients receiving EVT with no increased risk of symptomatic intracranial hemorrhage (SICH) within the 24-hour period after EVT. Hypothesis I-b: C-tDCS will not increase the rates of asymptomatic intracranial hemorrhage, early neurological deterioration (NIHSS during the 24-hour period after stimulation), 90-day mortality, and all serious adverse events. Hypothesis I-c: Majority of AIS patients ($\geq 90\%$) will tolerate the C-tDCS by completing at least 75% of the stimulation period with no major stimulation related pain, discomfort and skin changes.

Specific Aim II: To determine the feasibility of delivering C-tDCS as an adjunct and bridge to EVT.

Hypothesis II-a: Adjunctive C-tDCS after endovascular thrombectomy will be started more rapidly after the end of ET procedure over the course of the study and in the last 10 patients, median time from end of ET procedure to C-tDCS initiation will be ≤ 10 minutes. Hypothesis II-b: Bridging C-tDCS prior to endovascular thrombectomy will be started more rapidly over the course of the study and in the last 4 patients, median time from randomization to C-tDCS initiation will be ≤ 10 minutes.

Specific Aim III: To explore the potential imaging and clinical efficacy of tDCS in AIS as an adjunct and bridge to EVT.

1) Early and late penumbral salvage, defined as proportion of penumbral tissue on baseline multimodal MRI that does not proceed to infarct on 2-hour and 24-hour MRI (PWI); 2) Early and late collateral enhancement, evidenced by reduced perfusion lesion volume on 2-hour and 24-hour perfusion-weighted MRI (PWI); 3) Early and late reduction in infarct growth from baseline to 2-hour and 24-hour MRI; 4) Early improvement in neurologic deficit (NIHSS at 24h); 5) Improvement in final 3-month disability and quality of life (modified Rankin scale, AMC Linear Disability Scale, EQ-5D, and Barthel Index)

Impact

This in-hospital safety trial, will identify C-tDCS dose regimens that are feasible, well-tolerated, and preliminarily safe in patients with acute ischemic stroke who undergo ET. Study finding will identify the most promising dose regimens to advance to phase 2b and pivotal phase 3 efficacy trials for three patient populations with pressing need for improved therapies: 1) thrombectomy-eligible patients arriving directly to thrombectomy-capable hospitals who would benefit from post-arrival brain protection; 2) thrombectomy-eligible patients arriving initially

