The study sample size derives from the use of the 3+3, rule-based, modified Fibonacci, dose escalation design, with 3:1 randomization to active treatment vs sham control. There will be 6 dose tiers, reflecting increasing intensity and duration of stimulation (Figure 7). The 3+3 study design (3 patients and 1 sham) with 6 dose tiers yields a sample size of at least 24 and potentially up to 48. The 3+3 design is the classical approach to dose escalation in first-in-human studies.^{47,48} While newer, adaptive designs for dose escalation trials have been developed, they are more complex and have limited advantages when major toxicities are not expected.⁴⁹ Therefore, the rule-based, 3+3 design remains the dominantly employed approach in current dose-escalation studies. We will take every step to avoid missing data by scheduling of the follow-up visits early in visit time windows and readiness to travel to the patient's location to perform needed assessments. Should any missing data occur, primary analyses will be performed using multiple imputation, with sensitivity analyses including complete case and worst possible outcome analyses.⁵⁰

E.2.2. Baseline characteristics

The demographic and baseline clinical characteristics of the study population will be delineated with standard descriptive statistics. Categorical variables describing the clinical history, examination findings, and initial treatment will be summarized by frequencies. Continuous variables such as vital signs, laboratory results, and time variables will be characterized by means, standard deviations, and 95% confidence intervals (CI). Ordinal and non-normally distributed variables (such as the NIHSS) will be characterized by medians and interquartile ranges. Baseline characteristics will be compared between the tDCS stimulation group with sham group to assess covariate balance. Wilcoxon Rank-Sum tests will be used for continuous or ordinal variables; Fisher's exact tests and chi-square tests will be used for grouped or nominal categorical variables.

E.2.3. Safety and Tolerability (Specific Aim 1)

E.2.3.1 Dose Escalation

The study Data and Safety Monitoring Board (DSMB) will meet at the completion of each dose tier, review all safety data, and determine whether the study will proceed to the next dose tier. DSMB deliberations will be

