guided by: 1) a formal stopping/escalation rule, based on the occurrence of the lead safety endpoint, symptomatic intracranial hemorrhage (SICH), and 2) The DSMB members' clinical judgement upon review of all other safety outcomes. The formal dose escalation rule uses SICH frequency to gate the occurrence and pace of escalation through the 6 dose tiers. If no SICH occurs in the 3 active patients at a dose tier, enrollment may escalate to the next dose tier. If one SICH occurs, 3 more active (and 1 more control) patient will be enrolled at that dose tier before escalation. If 2 SICHs occur at a dose tier, further study enrollment is held until detailed review by the DSMB (Fig 6). In addition, whenever the formal SICH criteria for dose escalation has been met, the DSMB will formally meet, review the SICH data and all other safety data, and advice regarding proceeding to the next tier, continuing at the current tier, or placing the study on hold.

E.2.3.2. Primary Safety Endpoint Analysis

For the final statistical analysis of the primary SICH safety endpoint, a chi-square test will be used to detect differences in the rate of SICH between the active treatment and sham patients and higher and lower dose tiers. The treatment will be considered to have exhibited adequate safety in the current trial to proceed to future, larger, pivotal efficacy trials if tDCS results in lower or equivalent rates of SICH compared to sham.

E.2.3.3. Secondary Safety Endpoints Analysis

In secondary safety endpoint analyses, the following will be compared between the active treatment and sham patients, and between higher and lower dose tiers, using chi-squared tests: **1)** Asymptomatic ICH by 24h (intracranial hemorrhage not associated with NIHSS worsening ≥ 4); **2)** Early neurologic deterioration (worsening ≥ 4 on NIHSS during the 24-hour period after stimulation, with or without intracranial hemorrhage); **3)** All-cause mortality at day 90 (mRS); and **4)** All serious adverse events.

E.3.3. Tolerability Endpoint Analysis

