The lead tolerability endpoint is completion of the protocol-assigned stimulation treatment without early cessation due to cutaneous, neurologic, nociceptive or other adverse effects. Experience with tDCS in post-stroke patients indicates only infrequent cutaneous (itching, tingling) adverse effects are likely to occur. Accordingly, for the current study, a patient will be considered to have tolerated the procedure if at least 75% of the stimulus period was completed. The treatment will be considered generally tolerable if, among all enrolled patients, tolerated procedures are achieved in $\geq 90\%$ of patients, assessed with a one-sided p value of 0.025. Secondary tolerability endpoints will be the rate and severity of cutaneous, neurological, and pain items of the technician-filled (Figure 7), descriptively compared between active treatment and sham patients, and between higher and lower dose tiers.

E.3.4. Feasibility Endpoint Analysis (Specific Aim 2)

A time-motion analysis and mock run-throughs will be conducted prior to first enrollment. Nonetheless, it is anticipated that processes to optimize rapid placement of the cap and electrodes will continue to improve with experience gained from initially enrolled patients. The predefined success threshold for feasibility will be median times from randomization to bridging C-tDCS initiation and the time from end of EVT procedure to adjunctive C-tDCS initiation ≤ 10 minutes in the last 4 and 10 enrolled patients, respectively.

E.3.5. Exploratory Efficacy Endpoints Analysis (Specific Aim 3)

E.3.5.1. Exploratory Clinical Efficacy Endpoints

This study is underpowered to definitively determine efficacy, so all clinical efficacy analyses will be purely exploratory and descriptive. Four clinical outcome measures were selected based on their reliability, familiarity to the neurologic community, and adaptability for use in patients who have had a stroke. These endpoints are: the modified Rankin Scale (mRS), a rating of global disability; the Barthel Index (BI), a measure of instrumental activities of daily living; the National Institutes of Health Stroke Scale (NIHSS), a measure of neurologic deficit severity; and the EuroQol (EQ-5D), an assessment of health-related quality of life; and AMC Linear Disability Scale, a granular degree of disability.

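### Hypothesis I-b claims no increase in four secondary safety outcomes, but E.2.3.3 offers only chi-squared tests on 18 v 6 to 36 v 12 patients, with no margin or interval, so non-significance cannot support it

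*Combined protocol and SAP*

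**What the plan says.** Hypothesis I-b (section A, Specific Aim I) asserts that "C-tDCS will not increase the rates of asymptomatic intracranial hemorrhage, early neurological deterioration", and extends the same claim to 90-day mortality and all serious adverse events. The analysis is in E.2.3.3, where "the following will be compared between the active treatment and sham patients, and between higher and lower dose tiers, using chi-squared tests". That section gives no significance level, sidedness, non-inferiority margin, confidence interval or small-sample method.

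On size, E.2.1 says that the design "with 6 dose tiers yields a sample size of at least 24 and potentially up to 48", under "3:1 randomization to active treatment vs sham control". E.2.3.1 adds that after one symptomatic hemorrhage in a tier "3 more active (and 1 more control) patient will be enrolled at that dose tier before escalation".

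Three other places bear on the point:

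- E.2.2 names Fisher's test, but for baseline tables only: "exact tests and chi-square tests will be used for grouped or nominal categorical variables".
- E.3.5.1 gives the binary efficacy outcome (functional independence at 90 days) a rate with a 95% confidence interval. No safety outcome gets one. The statement that the study is underpowered appears in E.3.5.1 and E.3.5.2, for efficacy only.
- The one test level in the plan belongs to tolerability (E.3.3): "assessed with a one-sided p value of 0.025".

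**The concern.** A claim of no increase needs either a margin to test against or an interval showing how large an increase the data leave open. E.2.3.3 supplies neither. Its only product is a p value from a test of difference, and in a sample this small such a test will usually be non-significant whether or not stimulation does harm. If that result were read as confirming Hypothesis I-b, the trial would report reassurance that its data do not contain.

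According to D.6.10.2, the decision on further development draws on all outcome measures, so these four endpoints feed into it. E.2.3.2 deals separately with symptomatic hemorrhage and has its own criterion, so amending that section would leave E.2.3.3 and Hypothesis I-b as they are.

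**Working it through.** **Sample size (the plan's own figure).** 6 tiers × (3 active + 1 sham) = 24, that is 18 v 6. If every tier is expanded, 6 × (6 + 2) = 48, that is 36 v 12. Both agree with E.2.1.

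**Assumptions.** The plan states no level, sidedness or event rates for these endpoints. I take two-sided 0.05, Pearson's test without continuity correction, and event rates of 10% to 60%. Expected sham events at rates of 10% to 30% are 6 × 0.10 = 0.6 to 6 × 0.30 = 1.8, or 1.2 to 3.6 with 12 sham patients.

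**Single tables at 18 v 6.** For a/18 active and c/6 sham events, with b and d the patients without events, X² = N(ad − bc)² / [18 × 6 × (a + c) × (b + d)].

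- 7/18 v 0/6: 24 × 42² / (18 × 6 × 7 × 17) = 3.29, p = 0.070.
- 8/18 v 0/6: 24 × 48² / (18 × 6 × 8 × 16) = 4.00, p = 0.0455. With no sham events, 8 of 18 active patients (44%) must have an event before the test flags harm. With one sham event, 12/18 are needed.
- 0/18 v 2/6: 24 × 36² / (18 × 6 × 2 × 22) = 6.55, p = 0.011. Yates' correction gives p = 0.088. Fisher gives C(6,2)/C(24,2) = 15/276 = 0.054.
- 1/18 v 2/6: 24 × 30² / (18 × 6 × 3 × 21) = 3.17, p = 0.075.

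**Power to flag harm.** This is the sum of binomial probabilities over all tables with p < 0.05 and the higher rate in the active arm.

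| Sham to active rate | Pearson, 18 v 6 | Fisher, 18 v 6 | Pearson, 36 v 12 |
|---|---|---|---|
| 10% to 20% | 0.9% | 0.05% | 5% |
| 20% to 40% | 12% | 3.6% | 24% |
| 30% to 60% | 26% | 13% | 46% |

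Fisher at 18 v 6 needs 10/18 against 0/6.

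**Direction of false rejections.** Equal true rates, Pearson, 18 v 6:

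| True rate | Active worse | Sham worse | Total |
|---|---|---|---|
| 10% | 0.01% | 2.7% | 2.7% |
| 20% | 0.4% | 3.9% | 4.3% |
| 30% | 1.7% | 4.0% | 5.7% |
| 50% | 2.7% | 2.7% | 5.4% |

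**What equal observed rates would show.** Newcombe's interval combines the Wilson limits (l, u) of each arm, with arm 1 active and arm 2 sham: lower limit = d − √[(p1 − l1)² + (u2 − p2)²], upper limit = d + √[(u1 − p1)² + (p2 − l2)²]. For 3/18 the Wilson limits are 0.058 and 0.392; for 1/6 they are 0.030 and 0.564. With d = 0:

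- lower: −√(0.108² + 0.397²) = −0.41
- upper: √(0.226² + 0.137²) = 0.26

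For 6/36 v 2/12 the same method gives about −29 to +19 points.

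**The case against.** The strongest reply is that nothing in E.2.3.3 turns a non-significant result into a finding of safety. It says that the endpoints will be compared and sets no success rule; the safety criterion for proceeding is in E.2.3.2 and concerns symptomatic hemorrhage. The monitoring board reviews all safety data after each tier and applies clinical judgement (E.1, E.2.3.1), and D.6.10.2 rests the later decision on all outcomes. This stands. A reader might infer that no increase would be declared by default, or that harm during the trial would go unnoticed; the documents support neither. What remains is that Hypothesis I-b makes the claim and the only analysis stated for it cannot bear it.

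A reader might also infer that the test generally calls two sham events significant, or that the chi-squared test is badly invalid here. Neither holds. Two sham events reach p = 0.011 only with no active events and no continuity correction. At equal true rates the chance of exactly that table is 1.5% at a 10% rate and 0.4% at 20%. Expected counts are small, but total type I error stays near nominal, and the lean towards sham worse fades as events become common.

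Nor is the choice of test the cause of the low power. The cause is 24 to 48 patients in a 3+3 design, and Fisher's test flags harm less often still. Finally, the 3:1 argument does not extend to the comparison of higher with lower tiers. E.2.3.3 does not define that split; an even one at the minimum size would give 9 v 9 active patients.

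**Conclusion.** The point holds in this form: the analysis planned for the four secondary safety outcomes cannot support Hypothesis I-b. At 18 v 6 the chance of flagging a doubled rate is 0.9% to 26% over the rates examined. At 36 v 12 it is 5% to 46%. Equal observed rates of about 17% would leave an increase of 26 points open at the minimum size and 19 points at the maximum. For rare endpoints the few rejections that occur lean towards sham worse; this is a secondary matter.

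The power figures depend on the assumed level, test form and event rates. The intervals depend only on the illustrative counts and the method. The absence of a margin and of an interval is a matter of the plan's text and needs no assumption. Board review and the all-outcomes judgement limit the consequence, so this is a change that should be made rather than a fault that endangers the trial.

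**What to change.** 1. In E.2.3.3, make the main report the counts and rates per arm for each endpoint, with a 95% confidence interval (exact or Newcombe) for the active-minus-sham difference. E.3.5.1 already plans intervals for the binary efficacy outcome.
2. Reword Hypothesis I-b so that the aim is to estimate the difference and to state the largest increase that the data do not exclude.
3. State in E.2.3.3 that a non-significant result is not evidence of no increase.
4. If a p value is kept, take it from an exact test (Fisher, already named in E.2.2, or an exact unconditional test) and label it a descriptive supplement. Disclose that Fisher moves 0/18 v 2/6 to p = 0.054 but makes harm harder to flag: 10/18 is needed against 0/6, and power for 20% to 40% is 3.6% at 18 v 6. Changing the test alone would not repair the point.

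This is wording only. It adds no patients, visits or data and leaves the escalation rule untouched. The cost is that the safety statement will read less favourably.

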Stroke is a devastating condition and continues to be a leading cause of adult death and disability.¹ Endovascular thrombectomy (ET) has become standard of care for acute ischemic stroke due to large vessel occlusion.² However, ET has limitations that would be aided by neuroprotective interventions. ET fails to achieve substantial reperfusion in 20-30% of patient. Even among reperfusing patients, rates of excellent outcome are low - only 20-25% achieve freedom from disability (modified Rankin Scale 0-1), due to infarct growth prior to reperfusion and delayed and reperfusion injury after reperfusion.³⁻⁵ Therefore, bridging neuroprotective therapies prior to ET, can preserve more viable penumbra to rescue intervention by reperfusion and, therefore, enhancing its clinical benefit. While adjunctive neuroprotective strategies after ET can protect the brain against reperfusion injury and infarct growth due to incomplete reperfusion.⁶

Multiple candidate neuroprotective agents have failed in translation from animal to human studies.^{7,8} Amongst the missing intervention properties in the failed neuroprotection trials, two offer the most significant prospect of success: 1) having a pleiotropic effect, interdicting multiple pathways in the ischemic cascade, and 2) delivery by a direct transcranial, rather than intravascular, route, with fast and direct delivery to neural tissues regardless of cerebral perfusion. Transcranial direct current stimulation (tDCS) offers promise as just such an approach. In pre-clinical acute ischemic stroke models, cathodal tDCS (C-tDCS) applied to the ischemic hemisphere, has been shown to have a substantial neuroprotective effect with widely pleiotropic neuroprotective molecular mechanisms of action and can be delivered to the salvageable ischemic tissue beyond the occlusive thrombus despite reduced blood flow.^{9,10}

This study proposes to conduct the first-in-human, sham-controlled, dose-escalation, safety, feasibility, and potential efficacy trial of C-tDCS as a bridging and adjunctive neuroprotection before and after thrombectomy in acute ischemic stroke. To fully assess the potential safety aspects of adjunct C-tDCS to ET, we will exclude patients who receive intravenous thrombolysis.

Specific Aim I: To establish the safety and tolerability of C-tDCS in AIS as an adjunct and bridge to endovascular thrombectomy (EVT).

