This proposal is a prospective, single-center, dose-escalation safety, tolerability and feasibility study of C-tDCS as adjunctive and bridging neuroprotection in acute stroke patients undergoing endovascular thrombectomy. Patients with less than a complete EVT reperfusion (the thrombolysis in cerebral infarction (TICI) grading of <2c and 3) will be receiving at least one cycle of adjunct C-tDCS after EVT and at higher dose tiers, one cycle of bridging C-tDCS will be administered before EVT and if EVT results in TICI < 2c/3, then two cycles of adjunct EVT will be applied after EVT. The primary safety endpoints will be symptomatic intracranial hemorrhage during the 24-hour period after thrombectomy. Secondary measures of safety will include asymptomatic intracranial hemorrhage, early neurological deterioration, 3-month mortality and all serious adverse events. Tolerability will be judged based on the percentage of the patients completing the protocol-assigned stimulation treatment and secondarily, the rate and severity of cutaneous, neurologic, nociceptive or

other adverse effects will be assessed. Feasibility endpoints will analyze the speed with which tDCS will be implemented. Finally, we will explore signals of potential efficacy by examining the imaging evidence of infarct growth, and clinical outcomes of early neurologic deficit evolution, and 3-month global disability and health-related quality of life.

D2. Technology

D2.1. tDCS Device and Stimulation Parameters

The study will employ a Soterix™ high-definition DC-Stimulator, owned by the principal investigator. This tDCS unit consists of a stimulator, 4x1 HD interface and an adjustable cap with pre-maid openings that quickly and easily fits different head sizes. (Figure 5). The cap will be loaded with plastic electrode holders. These will be filled with conductance gel (Signa® gel), 1 cm² electrodes will be placed in the holders, and the holder then locked.

D2.2. Montage

The electrode positioning montage will be a 4 to 1-ring configuration, with the center or active electrode connected to cathode and the 4 reference or return electrodes connected to anode. The 4 to 1-ring configuration is chosen to focus the stimulation to the penumbral region. (Fig 6)

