We will implement a traditional 3+3 (rule-based, modified Fibonacci) dose escalation design, with 3:1 randomization to active treatment vs sham control. There will be 6 dose tiers, reflecting increasing intensity and duration of stimulation:

Tier 1 – 1 mA, single 20 - min cycle, will start at the conclusion of the EVT procedure in patients with less than a complete EVT recanalization (the thrombolysis in cerebral infarction (TICI) grading of <2c and 3) and negative immediate post-EVT CT scan for a definitive evidence of intracranial hemorrhage (ICH).

Tier 2 – 2 mA, single 20 min cycle, will start at the conclusion of the EVT procedure in patients with TICI<2c and 3 and negative immediate post-EVT CT scan for a definitive evidence of ICH.

Tier 3 – 1 mA, in 2 treatment cycles. First cycle will be a 20 min cycle, administered after the conclusion of the EVT procedure in patients with TICI<2c and 3 and negative immediate post-EVT CT scan for a definitive evidence of ICH. The second cycle will start 20 minutes after the end of the first cycle, and will last 20 minutes.

Tier 4 – 2 mA, in 2 treatment cycles. First cycle will be a 20 min cycle, administered after the conclusion of the EVT procedure in patients with TICI<2c and 3 and negative immediate post-EVT CT scan for a definitive evidence of ICH. The second cycle will start 20 minutes after the end of the first cycle, and will last 20 minutes.

Tier 5 - 1 mA, in 3 treatment cycles. First cycle will be a 20 min cycle, administered after initial imaging either in the Roland Reagan Medical Center or mobile stroke unit and prior to arterial puncture (cycle will be shorter than 20 minutes if EVT puncture is ready to proceed, in order not to delay EVT). The second cycle will start at the conclusion of the EVT procedure in patients with TICI<2c and 3 and negative immediate post-EVT CT scan for a definitive evidence of ICH (and not sooner than 20 minutes after the end of the first cycle), and will last 20 minutes. The third cycle will start 20 minutes after the end of the second cycle, and will last 20 minutes.

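### Tolerability is defined inconsistently and its 75% denominator is undefined, so a tier 5-6 patient given only the bridging cycle can score 33% or 100%

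*Combined protocol and SAP*

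**What the plan says.** Four statements of the tolerability rule appear.

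- Section A, Hypothesis I-c: "completing at least 75% of the stimulation period with no major stimulation related pain, discomfort and skin changes".
- D.1 Study overview: "Tolerability will be judged based on the percentage of the patients completing the protocol-assigned stimulation treatment". It gives no 75% threshold and no reason for stopping.
- E.3.3, lead endpoint: "completion of the protocol-assigned stimulation treatment without early cessation due to cutaneous, neurologic, nociceptive or other adverse effects".
- E.3.3, per-patient rule: "a patient will be considered to have tolerated the procedure if at least 75% of the stimulus period was completed". It gives no reason for stopping.

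E.3.3 calls the treatment tolerable if "among all enrolled patients, tolerated procedures are achieved in" at least 90%, and adds a one-sided p of 0.025. The sham arm wears the cap and electrodes but receives no current (D.4, Dose Tiers and Randomization).

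Tiers 5 and 6 plan three 20-minute cycles. The first is a bridging cycle before arterial puncture, and the "cycle will be shorter than 20 minutes if EVT puncture is ready to proceed, in order not to delay EVT". The other two are conditional: "The second cycle will start at the conclusion of the EVT procedure in patients with TICI<2c and 3 and negative immediate post-EVT CT scan" (the third cycle follows the second). Criterion 10 of D.3.1 admits these patients because they are undergoing thrombectomy, so they enter before its result is known. The opening overview table lists incomplete reperfusion without limiting it to a tier, but D.1, criteria 9 and 10 and the legend to Figure 7 make it a condition of the adjunctive cycles. Patients who receive bridging only are therefore an expected result of the design.

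**The concern.** Tolerability is a named success criterion under Aim I, and the four statements are not equivalent. Neither 'stimulus period' nor 'stimulation period' is defined as the tier's planned minutes or as the minutes triggered for the patient. Read literally against planned minutes, the 75% sentence would score a good reperfusion result as intolerance of the device.

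Two related weaknesses affect what the criterion measures. Sham patients cannot fail because of current, yet they count toward the 90%. And E.3.4 takes the adjunctive start-time median over the last 10 enrolled, although a bridging-only patient has no adjunctive start time.

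**Working it through.** **Sample size (E.2.1), reproduced.** 6 tiers × (3 active + 1 sham) = 24; with every tier expanded once, 6 × (6 + 2) = 48. Tiers 5-6 hold 8 of 24 or 16 of 48. Active patients at the minimum: 6 × 3 = 18.

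**The four statements applied to three patients.**

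| Patient | I-c | D.1 | E.3.3 lead | E.3.3 75% rule |
|---|---|---|---|---|
| Tier 5-6, full bridging, adjunctive cycles not triggered, no adverse effect | depends on denominator | depends on what counts as assigned | pass on the natural reading | depends on denominator |
| Tier 1, stopped at 16 of 20 min (80%) for a severe skin reaction | fail | fail | fail | pass |
| Completes everything, with major pain | fail | pass | pass | pass |

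**Score in tiers 5-6.** Planned minutes are 3 × 20 = 60, and 75% of 60 is 45.

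- Full bridging only: 20/60 = 33.3% (fail) or 20/20 = 100% (pass).
- Bridging cut for puncture, both adjunctive cycles completed: 5 min gives 45/60 = 75.0% (pass); 4 min gives 44/60 = 73.3% (fail).
- Bridging only and cut for puncture: 15 min gives 15/20 = 75% of the scheduled cycle; anything shorter fails even against 20 min.

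**Pooling sham.** Two failures, both active: 22/24 = 91.7% meets 90%, while 16/18 = 88.9% does not.

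**90% as a bare point threshold, 60-minute denominator.** At N = 24, two failures pass (22/24 = 91.7%) and three do not (21/24 = 87.5%). With withholding rate w, the chance that withholding alone misses the target is P(X ≥ 3), X ~ Bin(8, w). At N = 48, four failures pass (44/48 = 91.7%) and five do not (43/48 = 89.6%), so it is P(X ≥ 5), X ~ Bin(16, w).

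| Assumed w | 10% | 20% | 30% | 50% | 70% |
|---|---|---|---|---|---|
| N = 24 | 4% | 20% | 45% | 86% | 99% |
| N = 48 | not run | 20% | 55% | 96% | over 99% |

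The documents give no value for w. The nearest figure, in Section A, is "ET fails to achieve substantial reperfusion in 20-30% of patient". Section B labels TICI 2b as substantial, so the share reaching 2c or 3 is at most 1 − 0.20 = 80% to 1 − 0.30 = 70%. That caps the TICI part of w but sets no lower limit.

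**90% as an exact one-sided test that the rate exceeds 90%, p ≤ 0.025.** At N = 24, 24/24 gives 0.9^24 = 0.080, so no result succeeds. At N = 48, 48/48 gives 0.9^48 = 0.006 and 47/48 gives 0.040, so only 48/48 succeeds. For 18 active patients, 0.9^18 = 0.150.

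**E.3.4.** At N = 24 with tiers filled in order, the last 10 enrolled are 8 from tiers 5-6 and 2 from tier 4.

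**The case against.** The best defense is that the failing score needs a strained reading. The lead endpoint concerns early stopping for adverse effects, and the 75% sentence follows from it by way of 'Accordingly'. D.4 writes the TICI and CT conditions, and the puncture cut, into the tier 5-6 assignment itself. On that view a cycle never triggered was neither assigned nor stopped early, and the patient passes. This stands as the more natural reading. It does not settle the matter, because the operative sentence names no cause, D.1 names none either, and Hypothesis I-c adds a pain and skin condition that E.3.3 lacks.

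A reader might infer from the table that the trial will probably miss its tolerability target. The documents do not support that. The withholding rates are assumed, and the percentages belong to a point threshold with a 60-minute denominator. They do not carry over to the stated p of 0.025: on an exact test that the rate exceeds 90%, N = 24 fails whichever denominator is used. If the p-value were instead meant to show a rate below 90%, seven failures in 24 would be needed (six gives p = 0.028, seven gives 0.0075), and seven or more of eight tier 5-6 patients withheld has probability 3.5% at w = 50%.

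A reader might also infer that the adverse-effect reading removes these failures entirely. It does so for TICI withholding only. Hemorrhage on the CT after active bridging could fall under 'other adverse effects'. Nothing in the plan suggests that anyone intends to choose the denominator after seeing the data; it simply leaves the choice open.

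**Conclusion.** The inconsistency is real. A patient who completes bridging, has no adjunctive cycle triggered and has no adverse effect scores 33% or 100% depending on an undefined denominator; this needs no assumption about rates. The sham dilution (91.7% against 88.9%) is also plain arithmetic, for the case in which both failures are active.

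The trial-level effect is conditional. If 90% is a point threshold and planned minutes are the denominator, three bridging-only failures among eight miss the target at N = 24. If 90% is an exact test of a rate above 90%, the denominator is irrelevant at N = 24. At N = 48 one such failure decides the result. The plan does not say which is meant.

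Severity is minor to moderate. The formal escalation rule rests on symptomatic hemorrhage, with DSMB judgment on other safety outcomes, and D.6.10.2 leaves further development to an assessment of all outcomes together.

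**What to change.** 1. Use one definition in Hypothesis I-c, D.1 and E.3.3. The denominator is the stimulation triggered for that patient, excluding cycles withheld for TICI 2c/3 and time cut for puncture. Non-tolerated means stopped before 75% of that because of an adverse effect, or major stimulation-related pain, discomfort or skin changes. State which severity grade on the tolerability form counts as major. Do not count patients withheld for hemorrhage on the post-thrombectomy CT as tolerated by default: report them as a separate category and show the rate with them counted both ways.

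2. Apply the 90% criterion to active patients. Give the all-enrolled rate and a 60-minute-denominator analysis as sensitivity analyses. State whether 90% is a point threshold or a test; an exact test of a rate above 90% cannot succeed with 18 or 24 patients.

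3. In E.3.4, take the adjunctive median over the last 10 patients who started an adjunctive session, and say what counts as the start for sham.

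Whether bridging-only patients count among the three active patients in E.2.3.1 is a separate point. D.4 and E.2.3.1 must be reconciled; no rule is proposed here.

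The cost is mostly wording plus two sensitivity analyses. The tolerability form already records severity and whether an event shortened stimulation, but start and stop times are needed for every cycle: D.6.4 lists only the time bridging was aborted, and D.6.3 lists none. Two downsides remain. Very short bridging sessions appear as failures only in the sensitivity analysis. The active-only denominator is also smaller: with 18 patients, one failure passes (17/18 = 94.4%) and two do not (16/18 = 88.9%).
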